## **1. Purpose of the Study and Background**

### **1.1 Purpose of the Study**

The primary aims of this study are to assess the feasibility, acceptability, and tolerability of a virtual reality (VR) behavioral activation (BA) treatment for individuals diagnosed with major depressive disorder (MDD). The secondary aim of this study is to explore the efficacy of using VR to deliver BA therapy to a clinical MDD population.

The primary hypothesis of this study is that VR is an acceptable, feasible, and safe way to deliver a BA intervention for individuals diagnosed with MDD. Acceptability will measure the participant's desire to continue using the VR treatment after the study ends, the participant's satisfaction with the VR treatment, the participant's use of the headset, and the participant's acceptance of VR treatment. Feasibility will look at how well VR can integrate into the BA therapy. Tolerability will measure simulator sickness and agitation while using the VR headset.

A secondary hypothesis is that VRBA will have stronger effects than BA treatment as usual or a waitlist control in treating individuals with MDD due to increased homework compliance. This is due to the research that has illustrated that homework compliance is one of the strongest predictors of treatment outcomes for BA. This hypothesis will be assessed by running t-tests comparing the change in PHQ-9 scores at timepoints across the three study arms.

This study will also comment on the following questions: Can one successfully deliver BA without the movement component, simulating just the experience of pleasure/ mastery? Does VRBA lead people to want to engage in real-life activities? Is the active ingredient of BA emotion or movement? Movement during the VRBA will be measured with the headset.

### **1.2 Study Significance**

Little to no research has been done to elucidate the role of VR technology in lieu of real-world behavioral activation. This study will lay the groundwork for future studies to examine the role that VR may play in improving mood in clinical populations that are unable to perform real-world behavioral activation because of physical and/or psychological limitations.

### **1.3 Background**

Major depressive disorder (MDD) is one of the most common mental disorders in the United States. The lifetime prevalence of MDD is estimated to be 12% (Kessler et al., 2011) and it is the 11th greatest cause of disability and mortality in the world (Murray et al., 2012). Current treatment includes both cognitive behavioral therapy (CBT) and pharmacological intervention. There is strong evidence for the efficacy of a very simple type of CBT for depression that requires no active cognitive abilities from participants and can be delivered by primary care providers. This type of therapy is called Behavioral Activation (BA) (Dimidjian et al., 2011). Research has shown BA to be more effective than cognitive therapy alone and equivalent to

medication for treating depression in participants (Dimidjian et al., 2006; Scogin et al., 2005; Spates, Pagoto, & Kalata, 2006). However, many participants are unable to complete BA therapy due to lack of access to trained providers, physical constraints, diminished motivation, or geographical or financial reasons. Increasing access to mental health care using technology such as a Virtual BA therapy may provide a solution to these barriers.

Behavioral Activation encourages participants to change their moods by changing behavior and increasing sensory stimulation and positive emotions. BA therapy begins with monitoring a participant's current activity and identifying positive activities that can be added into the participant's daily schedule. These pleasant activities can be as simple as soaking in a bathtub, going to the mall, lying on the beach, or going fishing. These activities are then scheduled into the participant's daily routine, and progress is tracked. The list of activities is modified as necessary and challenges and barriers are problem-solved for each participant.

Virtual Reality (VR) technology now allows one to create and experience realistic and immersive virtual environments in which people can move around freely and interact with their surroundings. Compared to other mediums, VR is a very effective tool for eliciting feelings of presence: the user's subjective feeling of being inside a virtual environment. In part because of its ability to elicit presence, VR has been leveraged to deliver mental health interventions, including exposure-based therapies for participants with anxiety. VR is ideal for exposure therapy because participants are realistically immersed in a feared environment that is tailored to match their specific phobias (Maples-Keller, Runnell, Kim, & Rothbaum, 2017). For similar reasons, VR may also be ideal for delivering BA therapy: individuals can be immersed in environments that evoke strong feelings of enjoyment, mastery, and pleasure. These environments can be tailored to match each individual's list of ideal, positive activities. VR may also be ideal for delivering BA because it makes an incredibly wide range of activities easily and immediately accessible and can include pleasurable activities that may be impossible to complete in the real world (e.g. scuba-diving the Great Barrier Reef).

Within a clinical MDD population, VR-BA may be especially ideal for individuals who lack the motivation to engage in real-world BA. In this setting, VR-BA may either replace or act as a steppingstone to real-world BA. Standardizing and operationalizing a BA treatment to be self-administered may also be a cost-effective way of preventing and treating MDD. This may be especially important in areas where access to care is a problem for MDD treatment.

## **2. Criteria for Subject Selection**

### **2.1 Number of Subjects:** 30

**2.2 Gender of Subjects:** All genders will be included and accepted in the study.

**2.3 Age of Subjects:** Participants must be over the age of 18 years old.

**2.4 Racial and Ethnic Origin:** No enrollment restrictions based on race or ethnicity.

### **2.5 Inclusion Criteria:**

1. Participant must meet DSM V criteria for MDD
2. 18 years of age or older
3. English speaking

### **2.6 Exclusion criteria**

1. Substance Use Disorders in past year
2. Any psychosis or bipolar I disorder
3. Any seizure in the last 6 months or untreated epilepsy
4. Current suicidal urges and intent
5. Current nonsuicidal self-injury or parasuicidal behavior

## **3. Methods and Procedures**

### **3.1 Procedure**

Participants will be recruited from the clinic waitlist or through the study flyer. A total of 30 participants will be recruited, about 10 participants per study arm. These participants will be given the contact information of the protocol director. Upon reaching out to the protocol director, an informational phone script will be read to determine study eligibility and subject interest.

If subjects are interested and present with symptoms of depression, they will be invited to Stanford School of Medicine, Department of Psychiatry & Behavioral Sciences for an intake session. This session will include obtaining informed consent, the Mini International Neuropsychiatric Interview, and completing the demographic questionnaire. If subjects meet study eligibility, they will be randomized into either the VRBA, BA treatment as usual, or waitlist control arm of the study using 5 opaque, concealed envelopes in sets of 6 to preserve balance throughout the study. Participants will have a 1 in 3 chance of being randomized into each group. Participants will then be scheduled for their first treatment appointment.

The VR intervention will follow the protocol for Behavioral Activation (BA). Participants in the BA treatment as usual or VRBA arms of the study will meet with their clinician once per week for 50 minutes to receive BA therapy. These participants will complete the PHQ-9 at the

beginning of each session. If item 9 is endorsed, a risk assessment will be completed in real-time and appropriate actions will be taken.

In the first session, psychoeducation around the connection between behavior and mood will be discussed. Participants will then be introduced to BA. Participants will consider activities they enjoy as well as be provided with an activity list. Participants will be asked to select at least four activities that are highly enjoyable to schedule into their upcoming week. The VRBA participants will be required to choose VR activities for the week and the BA treatment as usual participants will be required to choose real-life activities to participate in. The VR participants will complete an activity in VR during session, in order to learn how to use the headset, which they will take home. Each time the participant finishes an activity in VR, he/she will be asked to complete a questionnaire assessing “spatial presence,” “simulator sickness,” “agitation measure,” and acceptability. Participants will also be asked to rate their mood on a scale of 1-10 (1=worst they ever felt; 10=best they ever felt) before and after their chosen activity. During session 2 and 3, clinicians will check in regarding goal attainment, work on barriers to completion of activities, assess depression scores, and introduce a new activity goal. During session 4, the treatment and skills will be reviewed, and feedback will be attained.

The participants randomized to the waitlist control group will be administered the PHQ-9 via phone on a weekly basis for four weeks. If item 9 is endorsed, a risk assessment will be conducted in real-time, and proper measures will be taken in accordance with risk. After the four weeks are completed, these participants will be given the option to simply remain on the clinic waitlist or choose to partake in 4 weeks of VRBA or BA treatment as usual. Only the data during their time as a waitlist control will be used in the study.

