**Aim 2 Analysis:** In order to determine any initial clinical efficacy of the VR BA treatment compared to BA treatment as usual and a waitlist control, participants' depression scores were measured using the PHQ-9 at four time points. With the goal of randomizing 30 participants, the average change between PHQ-9 scores at time 4 and time 1 for each of the three groups were going to be compared to one another. Example: Average change in PHQ-9 scores of group A (VRBA) was going to be compared to the average change in PHQ-9 scores of group B (BA treatment as usual). The average change in PHQ-9 scores of group A was going to be compared to the average change in PHQ-9 scores of group C (waitlist control). The average change in PHQ-9 scores of group B was going to be compared to the average change in PHQ-9 scores of group C. This change was going to be determined using independent samples t-tests.

However, given the lower-than-expected sample size, in order to assess initial clinical efficacy of the VR BA treatment compared to the BA treatment as usual and control groups, each group's mean as well as each participant's PHQ-9 scores were graphically represented across time. Additionally, each group's mean PHQ-9 change scores from time one through time four were graphically represented.

**Exploratory Aim 1:** To evaluate whether engaging in an activity in VR increases mood more than engaging in an activity in real life.

**Exploratory Aim 1 Analysis:** In order to evaluate whether engaging in an activity in VR increased mood more than engaging in an activity in real life, the differences in mood before

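### Aim 2: no PHQ-9 is named before randomisation, so the change-score baseline most naturally falls after participants can know whether they are treated or waitlisted (minor risk; an intake PHQ-9 is a cheap improvement)

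*Protocol*

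**What the plan says.** Protocol 3.1 (Procedure) sets out the order of events. For the intake session: "This session will include obtaining informed consent, the Mini International Neuropsychiatric Interview, and completing the demographic questionnaire". Those who are eligible come next: "they will be randomized into either the VRBA, BA treatment as usual, or waitlist control arm of the study". After that, "Participants will then be scheduled for their first treatment appointment".

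The first PHQ-9 that the protocol names comes later. For the VRBA and BA arms, "These participants will complete the PHQ-9 at the" start of each weekly session. The waitlist group, already randomised, "will be administered the PHQ-9 via phone on a weekly basis for four weeks". The planned size is "about 10 participants per study arm".

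The SAP (Aim 2 Analysis) says depression was "measured using the PHQ-9 at four time points". The planned comparison used "the average change between PHQ-9 scores at time 4 and time 1 for each of the three groups", taken pairwise with t-tests. Because the sample fell short, the SAP replaced the tests with plots of individual and mean scores over time and of mean change from time 1 to time 4. Neither document describes blinding of participants, and neither defines time 1 by date.

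**The concern.** A change score is easiest to interpret when its baseline cannot have been affected by allocation. Here the baseline is a self-report that appears to be taken after allocation in an open trial. Some participants are recruited from the clinic waitlist, so learning that treatment starts now, or that it does not, could plausibly move the first score. If it moves the arms differently, every comparison that subtracts time 1 carries the difference. The direction is unknown: a treated-arm score pushed up relative to waitlist makes the benefit look larger, and one pushed down makes it look smaller.

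The plots do not escape this, because mean change is still measured from time 1. A reader who sees the arms differ at time 1 has no earlier score with which to separate chance imbalance from a reaction to allocation. Anyone who leaves between randomisation and time 1 has no depression score at all.

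**Working it through.** The documents give no effect size, SD or dropout rate for Aim 2, so there is no stated figure to reproduce. The check covers the order of events, then the algebra of the change score.

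**1. When is time 1?** There are four sessions in the treated arms, four weekly calls in the waitlist arm and four PHQ-9 time points in the SAP. An intake PHQ-9 would make five. The count therefore fits time 1 = session 1 or first call, both after randomisation.

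**2. What can participants know by then?** Waitlist participants receive phone calls and treated participants a clinic appointment, so treated versus waitlisted can be known. For VRBA versus BA the documents do not say when the therapy is named. Both arms complete the PHQ-9 at the start of session 1, before therapy content, in the same setting.

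**3. Effect of a shift at time 1.** Let T be the effect apart from the shift, D the between-arm difference at time 1 caused by knowing the allocation (treated minus waitlist), and f the share of D still present at time 4. Negative values favour treatment.

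- Total effect of allocation at time 4 = T + fD
- Contrast in time 4 minus time 1 = T + fD − D
- Contrast in time 4 minus intake = T + fD, since randomisation makes the expected intake difference 0

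With assumed T = −3 and D = 2:

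| f | Total effect | Time 1 baseline: contrast | error vs total | error vs T | Intake baseline: contrast | error vs total | error vs T |
|---|---|---|---|---|---|---|---|
| 0 | −3 | −5 | −2 | −2 | −3 | 0 | 0 |
| 0.5 | −2 | −4 | −2 | −1 | −2 | 0 | +1 |
| 1 | −1 | −3 | −2 | 0 | −1 | 0 | +2 |

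With D = −2 the totals are −3, −4, −5 and the time 1 contrasts −1, −2, −3, an error of +2 against the total each time. So the error is −D whatever f is, if the target is the total effect of allocation. Against T it depends on f, and at f = 1 the existing contrast is exact.

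**4. What an intake baseline would bring in.** Let m be a constant difference between phone and clinic collection. In the waitlist arm, time 4 minus time 1 is phone minus phone and m cancels. Time 4 minus intake is phone minus clinic and m stays, so each waitlist contrast moves by m; an assumed m of 1 point gives 1 point. As to interval, four weekly scores span three weekly gaps, about three weeks in every arm. From intake the span is about three weeks plus the gap to time 1, which is not fixed in any arm and may differ between treated and waitlist.

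**5. Missing baselines.** At 10 per planned arm, each person lost before time 1 is 1/10 = 10%. An assumed 0 to 2 per arm is 0 to 20% with no depression score.

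**The case against.** The strongest reply has four parts.

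First, the list of intake content need not be complete, time 1 is not defined, and the moment of disclosure is not stated. That stands as a limit on certainty. The match of four time points to four sessions or calls still makes a post-randomisation baseline the natural reading.

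Second, the size of the error depends on the target. The SAP asks about efficacy and does not name the total effect of allocation as its estimand. That stands, and step 3 shows both targets.

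Third, replacing time 1 with an intake score would let a constant phone effect and an unequal interval into both waitlist contrasts, where at present the phone effect cancels. That also stands. It argues for reporting both changes, not for leaving intake unmeasured.

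Fourth, an intake score does not give early leavers a change score. True; it gives them a baseline only.

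A reader might infer more: that the Aim 2 results are biased, that all three contrasts are affected alike, or that an intake baseline is simply better. The documents support none of these. They give no value or direction for D, nothing shows that VRBA and BA participants learn their therapy before the session 1 PHQ-9, and the mode and timing differences cut against a straight swap. Two further features are not bias in themselves: the time 4 score precedes the content of session 4, which only limits what is estimated, and phone collection affects the time 1 to time 4 change only if its effect varies with time or severity.

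**Conclusion.** The point holds as a minor risk. On the natural reading, the Aim 2 baseline follows open allocation. The two waitlist contrasts are the ones mainly exposed; VRBA versus BA is exposed only if the specific therapy is disclosed before session 1. For the total effect of allocation the error equals D in size: 0 if knowing the arm has no differential effect, and 1 to 3 points over an assumed range of 1 to 3. That range is illustrative. For the effect apart from the shift, the error runs from D in size down to nothing, depending on how much of the shift persists to time 4.

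The consequence is small. Efficacy is a secondary, exploratory aim, the t-tests were dropped in favour of graphs, and the primary aims do not use the PHQ-9.

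**What to change.** If the schedule can still be changed, or for a successor trial:

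- Give the PHQ-9 at the intake visit, in all arms, before the envelope is opened. Plot it as a pre-randomisation point.
- Report change from intake alongside the time 1 to time 4 change, not in place of it.
- Use one mode of collection across arms where possible. Otherwise state that a clinic-to-phone difference can enter the waitlist change from intake.
- Time the waitlist calls to match the session schedule, or report days from randomisation to time 1 and to time 4 by arm.

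Cost: one short questionnaire per participant (30 in all) on a form already in use, a line of protocol wording, and the mode and interval caveat.

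If data collection is complete, as the SAP's past tense suggests, the questionnaire cannot be added. State beside the plotted changes that time 1 appears to be post-randomisation, and report by arm the days from randomisation to time 1 and the number randomised without a time 1 score. The dropout rates that the SAP lists under Aim 1 concern VR feasibility and do not supply this. Cost: one sentence and two descriptive rows per arm.

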#### **4. Data Safety Monitoring Plan**

As this is a case series within standard of care procedures, steps to minimize risks to the confidentiality of identifiable information will be taken as with all HIPPA compliant services delivered at the Clinic. Data will all be labeled with the participants' assigned ID number. Protected Health Information will be kept separate from data and ID numbers in a Stanford University School of Medicine encrypted database to which only the PI and research assistants will have access. Psychological effects of study participation or breeches in confidentiality will be monitored and discussed at research meetings. There is a slight risk of motion sickness so participants will be closely monitored while immersed in the virtual scene, and if there is any discomfort they will be removed from the virtual environment. Participants are free to discontinue participation at any time. Any situation requiring medical attention will be promptly provided.

Given that participants enrolled are clinically depressed, suicidal ideation will be assessed each session. If it is revealed that a participant is expressing suicidal ideation, the clinician will conduct a thorough risk assessment in real time and a safety plan will be created. If it is determined the participant is an imminent danger to themselves, the clinician will initiate a 5150 hold and walk the participant to the hospital.

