# **Virtual Reality Behavioral Activation: An Intervention for Major Depressive Disorder**

**NCT04268316**

**April 13, 2021**

**Aim 1:** To evaluate whether using VR to administer a brief BA protocol is a feasible, acceptable, and tolerable treatment for individuals diagnosed with MDD.

**Aim 1 Analysis:** The feasibility, or degree to which VR could successfully be integrated into the brief BA protocol, was measured by commenting on qualitative barriers to use observed. Barriers were assessed by rates of dropout, adverse events, the number of times the headset was used, and the level of presence experienced in the headset, all of which were represented in a table, as recommended by Birkhead et al. (2019). Level of presence was obtained by participant report from a Likert scale of 0 (not at all) through 4 (very strongly) for each question; and with three questions, there was a possibility of yielding a score between 0 and 12. The average total presence for each participant, intend-to-treat (ITT) participants, and protocol completers were then calculated and placed into a table. The average presence experienced was also calculated as a percentage by dividing the average score by 12 (the maximum score). Acceptability of the VR BA treatment was measured by participant report using the TAM, with the agreeance choice on the Likert scale represented from 0 (strongly disagree) through 4 (strongly agree). The number of questions in each category determined the outcome range (either 0-12 for three questions or 0-16 for four questions). Each participant's scores were then averaged and placed into a table, along with the average ITT participants and protocol completers' scores. The average percentage of acceptance was also calculated by dividing the average score by the maximum score in the outcome range. In order to determine the degree of

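### The VR questionnaire is requested when an activity is finished and not expressly after an early stop, so the Aim 1 averages may leave out activities stopped for discomfort

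*Protocol*

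**What the plan says.** Protocol section 1.1 makes tolerability a primary aim and defines it: "Tolerability will measure simulator sickness and agitation while using the VR headset". The definition is not limited to completed activities.

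Protocol section 3.1 sets when the data are collected: "Each time the participant finishes an activity in VR, he/she will be asked to complete a questionnaire assessing" spatial presence, simulator sickness, agitation and acceptability. VRBA participants do one activity in session to "learn how to use the headset, which they will take home", so later activities can take place without staff present.

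Protocol section 4 covers discomfort: "if there is any discomfort they will be removed from the virtual environment". It does not mention the questionnaire at that point.

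The SAP (Aim 1 Analysis) takes presence, acceptability (TAM), physical tolerability (SSQ) and emotional tolerability (BAM) from participant report. It averages each participant's scores and then reports averages for ITT participants and for protocol completers. It has no rule for activities stopped early or for missing forms. Feasibility is reported separately: it is "measured by commenting on qualitative barriers to use observed", with dropout, adverse events, headset-use counts and presence in a table.

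**The concern.** The event that could prevent a form from being requested, stopping because of discomfort, is close to what the form measures. If forms follow only completed activities, the tolerability averages are taken over a set from which the worst-tolerated activities are more likely to be missing. A participant who completed no activity would have no score at all.

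The ITT average does not repair this. ITT in the SAP describes which participants are averaged, not which activities, and it cannot include a score that was never collected. About 10 participants per arm were planned, and the SAP reports a smaller sample than expected, so one person's missing forms could move a table visibly.

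**Working it through.** **Plan's own figure.** The SAP's SSQ example scores three symptoms 1, 2 and 1. There are 16 items scored 0 to 3, so the maximum is 16 × 3 = 48. Then (1 + 2 + 1)/48 = 4/48 = 8.33% intolerability, and 100 − 8.33 = 91.67% tolerability. Both match the SAP. The scoring is not in dispute; the question is which activities receive a score.

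**Two readings of *finishes*.**

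| Reading | Form after an early stop? | Effect on Aim 1 averages |
|---|---|---|
| Any ending of the activity | Yes | None |
| Completion of the activity | Not requested | Stopped activities are left out |

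Neither document chooses between them. For the completion reading: section 3.1 elsewhere has clinicians "work on barriers to completion of activities", and the SAP's Exploratory Aim 1 divides mood change by the number of activities completed (a different outcome, so context only). For the any-ending reading: the SAP describes the tolerability percentage activity by activity and states no completion condition.

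**Form of the bias under the completion reading.** For participant i, let p_i be the share of started activities that were stopped, F_i the mean score of finished activities, S_i the mean score of stopped ones, and D_i = S_i − F_i. Then

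all-started mean − finished-only mean = (1 − p_i)F_i + p_i S_i − F_i = p_i D_i.

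- If p_i = 0 or D_i = 0, the difference is zero.
- If D_i is positive on the SSQ or BAM, the finished-only mean understates symptoms.
- If p_i = 1, the finished-only mean does not exist and the participant drops out of the average.
- The SAP averages within participant first. Among participants with at least one finished activity, the group mean therefore shifts by the average of p_i D_i, which depends on how stops cluster and not only on their total number.

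The same identity applies to each scale with its own maximum: 48 for the SSQ, 18 for the rescaled BAM, 12 for presence, and 12 or 16 for the TAM categories.

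**Inputs available.** The documents give neither p_i nor D_i for any scale, so the formula cannot be evaluated.

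**What other records would show.** Early stops could surface in dropout, adverse events, headset-use counts, qualitative barriers, the clinician's review in sessions 2 and 3, session 4 feedback, or the research-meeting review in protocol section 4. None of these is described as supplying a symptom score or a structured reason for stopping, and none is described as entering the SSQ, BAM, TAM or presence averages.

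**The case against.** The strongest objection is that everything rests on one undefined word. The sentence may be only a timing instruction, meaning after VR and not during it. The questionnaire itself is not in the documents, so its actual trigger cannot be checked. This stands: the point is an ambiguity to resolve, not a demonstrated omission.

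A second objection is that section 4 describes observed exposure, since "participants will be closely monitored while immersed in the virtual scene". Staff who remove a participant are present and can hand over the form. This also stands for in-session use. It does not cover a stop at home, where the participant must decide alone whether the activity counts as finished.

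Third, the signal need not be lost, because a stop for nausea could appear in several of the other records. That is fair, but it does not correct the averages that answer the tolerability aim.

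Fourth, Aim 1 is descriptive, with no test or threshold, and the SAP is in the past tense, so a change to collection is probably too late. Both are true. They limit the consequence and move the remedy to reporting.

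On monitoring, section 4 can be read as covering only the in-session activity. It does not say so, which is why the two sections need reconciling.

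**Conclusion.** The point holds in conditional form. If *finishes* was applied as completion, and if stopped activities score worse, the Aim 1 averages make VR look better tolerated than it was. That direction is plausible because discomfort is the stated trigger for removal. If either condition fails, there is no such overstatement. The size cannot be determined from the documents, no bound is claimed, and with no threshold set no conclusion is shown to change.

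Two stronger inferences are tempting and not supported. One is that the plan excludes stopped activities, or that tolerability was in fact overstated; the wording allows this but does not establish it. The other is a numerical share. Participants are "asked to select at least four activities that are highly enjoyable to schedule into their upcoming week", and a reader might take one stop as a quarter of the first week. But four is a minimum, the in-session activity also counts (exactly four scheduled, all started, gives 1/(4 + 1) = 20%, and less if more are scheduled), and scheduled activities are not necessarily started. No share follows from the text.

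This is worth considering and not a major defect: the possible bias runs mainly in one direction in a primary aim, and it is nearly costless to remove or expose.

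**What to change.** **If any collection remains:** state that the questionnaire is requested at the end of every VR activity started, whether finished or stopped, and add one item recording early stopping and its reason. Cost: a wording change and one item.

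**If collection is over, as the SAP's past tense suggests:**
1. Tabulate forms received beside headset uses for each VRBA participant. The use counts are already planned, and the form counts are new.
2. Give the n behind each ITT average.
3. State when the form was actually taken. If only after completed activities, say that the averages describe those only.

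Cost: a few table columns and one sentence.

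**Limits:** some forms for home activities will still be missing, and headset uses may not match assigned activities one to one, so a gap between the two counts suggests missing forms but does not prove them.

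**Separately:** protocol section 3.1 (take-home headset) and section 4 (close monitoring while immersed) must be reconciled.
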